2.3 Hypotheses

Hypothesis 1. We hypothesize that the study enrollment rate will be greater than in the original UV4.me efficacy study and that our sample will be representative of national demographics of young adults other than race/ethnicity (associated with skin cancer risk), indicating potential generalizability.

Hypothesis 2. We hypothesize that the UV4.me2 will be the most effective intervention, followed by UV4.me.

Hypothesis 3. We hypothesize that maintenance outcomes will be best in the UV4.me2 group, next best for UV4.me, and least for the e-pamphlet group.

Hypothesis 4. We hypothesize that greater intervention utilization (e.g., logins, module completion) and satisfaction will be associated with better behavioral outcomes

Hypothesis 5. We hypothesize that UV4.me2 and UV4.me will have higher incremental costs than the epamphlet. However, because UV4.me2 and UV4.me are also expected to result in better behavioral outcomes, we will assess cost-effectiveness to address whether these interventions are worth the additional costs.

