Enhanced UV4.me2: New features/strategies were chosen based on participant feedback from the original UV4.me grant (e.g., suggested strategies to make UV4.me more interactive), our data (e.g., number of mobile users who tried to access UV4.me), and reviews/models of effective e-Health interventions 65,66 and implementation strategies 69,70,72. Several enhancements are expected to improve reach, implementation, and behavioral outcomes simultaneously:

1. Mobile Site. A mobile version will likely improve reach directly because more people will have access and may improve effectiveness indirectly by facilitating ongoing implementation. The mobile platform will be developed for both Android and Apple devices.

2. Incentives. The enhanced UV4.me2 site will also offer incentives in the form of clickable coupons and links to free samples for sun protection products (e.g., sunscreen). Appropriately selected incentives generally reinforce behavioral implementation, retention, and health behavior change, including in online trials, especially among those initially least motivated and/or for behaviors that are not intrinsically enjoyable (e.g., applying sunscreen) 71,109-115. These incentives will be used to reinforce behavioral implementation, retention, and health behavior change.

3. Behavioral Tracking & Feedback. Users will be allowed to set goals and enter relevant behavioral events (e.g., sunbathing, indoor tanning, sunscreen use) over time and see them summarized graphically on the homepage and receive motivating feedback (e.g., "Great job, your tanning is going down over time!"). Behavior tracking and feedback are well-established empirically-supported behavior change techniques including for internet interventions 116,117. As with the original UV4.me site, participants will be able to set "alerts" to notify them (e.g., email, SMS texting) to remind them to work on their behavioral goals.

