
13.2 Statistical Analyses for Secondary Aims

Maintenance. We will compare baseline to 6- and 12-month changes in UV exposure and protection across study arms. Tests will be two-sided with a 5% type I error for these secondary analyses. We anticipate having follow-up data from approximately 960 and 768 participants at 6- and 12-months, respectively. This will allow for 154 participants in the e-pamphlet arm and 307 in each of the other two arms at 12 months. Detectable differences with 80% power are presented in Table 3.

Implementation. Using BeHealth's Wasabi data management system, we will create a summary index representing how frequently and for how long participants are logged into the interventions and how many sections are completed and determine whether this index is associated with behavioral outcomes. Whether and when a user accesses the e-pamphlet will be noted. We have experience using Google Analytics "goals" to track how frequently individual pages within modules are accessed. We will ask participants about their satisfaction with the study/intervention and selected components (e.g., the enhanced features) both from within the interventions and a one-month follow-up inquiry. These implementation variables will also be linked to participant source (i.e., skin protection organizations, Google Adwords, Facebook ads, consumer research panel) when possible so that sources can be compared in terms of participant intervention implementation. We will use the methods described for Aim 2 to compare these utilization and satisfaction measures across study arms, and Spearman's correlation to measure the level of association between implementation metrics and longitudinal changes in UV exposure and protection indexes within and across study arms. Tests will be two-sided with a 5% type I error for these secondary analyses. We anticipate 1350 participants at 1-month follow-up (epamphlet = 270, others = 540). Whether individuals click into the pages with discounts and free samples from skincare companies will be noted. We will assess whether accessing more incentives within the interventions is associated with greater intervention utilization and better behavioral outcomes.

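### The across-arm Spearman correlation for Hypothesis 4 can pick up the randomised arm difference, and the plan does not say whether the pooled or the within-arm result decides

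*Combined protocol and SAP*

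**What the plan says.** Hypothesis 4 (section 2.3) is that "greater intervention utilization (e.g., logins, module completion) and satisfaction will be associated with better behavioral outcomes". Section 13.2, under Implementation, builds a summary index from "how frequently and for how long participants are logged into the interventions and how many sections are completed". It then plans Spearman's correlation "to measure the level of association between implementation metrics and longitudinal changes in UV exposure and protection indexes within and across study arms". On error rate it says: "Tests will be two-sided with a 5% type I error for these secondary analyses".

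The section does not adjust the across-arm correlation for arm and does not rank the pooled and within-arm results. The Aim 2 regression methods, which include study arm as a covariate, are assigned to comparing utilization and satisfaction between arms. They are not assigned to the usage-outcome association.

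The protocol also states what it expects of the arms. For effectiveness, "UV4.me2 will be the most effective intervention, followed by UV4.me". For maintenance, "maintenance outcomes will be best in the UV4.me2 group, next best for UV4.me, and least for the e-pamphlet group". For the UV4.me2 features, section 4.3.1 says: "Several enhancements are expected to improve reach, implementation, and behavioral outcomes simultaneously". For the e-pamphlet, section 13.2 adds: "Whether and when a user accesses the e-pamphlet will be noted".

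**The concern.** A correlation computed over all participants together combines two things: the association inside each arm, and the association between arm means. If UV4.me2 participants use their site more and also improve more, the second part is positive even when heavy and light users within each arm do equally well. The pooled rho then partly repeats the randomised comparison already made under Aim 2, yet it is reported under a hypothesis about usage.

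The plan's own expectations point in the direction that creates this pattern. UV4.me is built from 12 modules, the e-pamphlet is non-interactive, and UV4.me2 is designed to raise implementation and behaviour together. A count of sections completed therefore does not mean the same thing in all three arms.

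Because no order of precedence is set, a significant pooled result could be presented as support for Hypothesis 4 while the within-arm results are null. What is at stake is the interpretation of one secondary aim. The primary outcomes and the sample size are not affected.

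**Working it through.** **Inputs from section 13.** Completers at 3 months: 480 (UV4.me2), 480 (UV4.me), 240 (e-pamphlet). Primary alpha 0.0125 two-sided, power 80%. Stated detectable effects: 0.22 SD (UV4.me2 v UV4.me) and 0.26 SD (UV4.me2 v e-pamphlet). Alpha for the Spearman tests: 0.05 two-sided.

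**Reproducing the plan's figures.** d = (z₀.₉₉₃₇₅ + z₀.₈₀) × √(1/n₁ + 1/n₂), with z sum 2.498 + 0.842 ≈ 3.339.
- 480 v 480: 3.339 × 0.06455 = 0.216 (stated 0.22).
- 480 v 240: 3.339 × 0.07906 = 0.264 (stated 0.26).

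**Outcome shifts.** Score the outcome so that higher is better and set the e-pamphlet at 0. UV4.me2 is then at 0.264 and UV4.me at 0.264 − 0.216 = 0.048. These are the plan's detectable sizes, not predictions.

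**Usage shifts.** The documents give none, so a range is assumed, in within-arm SD.

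**One case by hand.** Arm weights 0.4/0.4/0.2, usage means 1/0.5/0, no within-arm association, within-arm variance 1.
- Between-arm covariance: (0.4×1×0.264 + 0.4×0.5×0.048) − (0.6 × 0.1248) = 0.1152 − 0.0749 = 0.0403.
- Between-arm variances: usage 0.14, outcome 0.0132.
- Pooled correlation: 0.0403 / √(1.14 × 1.0132) = 0.0375 on the raw scale. The simulated Spearman mean is 0.036.
- Approximate test statistic: 0.036 × √1200 ≈ 1.25, so P(Z > 1.96 − 1.25) ≈ 0.24.

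**Simulation** (1,500 to 4,000 trials per scenario, usage and outcome independent within every arm):

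| Usage means (UV4.me2/UV4.me/e-pamphlet) | Mean pooled rho | Pooled test rejects | Arm-stratified test rejects |
|---|---|---|---|
| 0.4/0.2/0 | 0.015 | 8% | 4% |
| 1/0.5/0 | 0.036 | 23–25% | 4–5% |
| 1.5/1/0 | 0.045 | 32–34% | 4–5% |
| 3/2.5/0 | 0.056 | 50% | 4–5% |

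The stratified test averages the within-arm Fisher-z values, weighted by n − 3. Within-arm tests taken singly reject in about 5%. In the last three rows UV4.me2 is only 0.5 SD ahead of UV4.me. A wider gap between the two sites raises the figure: with near-identical outcome shifts (0.26/0.04/0), usage means of 2/1/0 give about 60% and 4/2/0 about 89%.

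**Leaving out the e-pamphlet.** Pooling only UV4.me2 and UV4.me, with an outcome difference of 0.22 SD, rejects in 6% to 68% as the usage difference runs from 0.2 to 2 SD. Removing the e-pamphlet alone does not cure the problem.

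**Controls.** When the arms differ in usage only, or in outcome only, the pooled test rejects in about 5%. Usage means 1/0.5/0 with outcome means 0.065/0.26/0 give mean rho 0.00 and about 5% rejection, although the arms differ in both.

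**The case against.** Hypothesis 4 is worded as an association, and the plan says Spearman will measure a level of association. It does not promise a causal usage effect. If the arms differ in both variables, a pooled association does exist, and if usage mediates the arm effect, part of it is genuine. The rejection rates above are therefore not type I error for the hypothesis as literally worded. They are error rates only if the result is read as saying that heavier users do better than lighter users given the same intervention. That stands. The pooled rho still cannot separate the two readings, and nothing tells the analyst which result to rely on.

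Within-arm correlations are planned in the same sentence and are free of this artefact. That also stands, and it reduces the defect to the missing arm adjustment and the missing order of precedence.

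A reader might infer that the e-pamphlet arm has no usage data beyond access. The documents do not establish this. Section 4.4.2 records logins to the interventions and mentions e-pamphlet access as an addition. Section 4.5 pays participants in each condition for a first login. Login counts may therefore exist in all three arms. Sections completed are the metric that does not carry over.

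**Conclusion.** The concern holds in a limited form. Under the same-direction arm pattern that the protocol expects, the pooled correlation mixes the randomised arm difference into the usage-outcome association, and the plan lets that result bear on Hypothesis 4 without adjustment or precedence. At the plan's detectable effects the rejection rate is about 8% for small usage gaps and 23–50% for the 1–3 SD scenarios tabulated, against about 5% for a stratified test. The correlations themselves are small.

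These figures rest on assumed usage gaps, on outcome shifts set at detectable rather than expected sizes, and on normal variables with equal spread in every arm.

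Two stronger readings are not supported. The first is that pooling always produces an association when arms differ in usage and outcome: a non-monotone pattern can cancel it, and a reversed order changes its sign. The second is that Hypothesis 4 would be supported whenever the intervention works: in the tabulated scenarios the pooled test is non-significant in about half of trials or more. Rates of 48–94% arise only with outcome shifts of 0.44/0.22/0 SD, and the 0.44 is not in the documents.

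**What to change.** State in section 13.2 that an arm-stratified (arm-adjusted partial) rank correlation decides Hypothesis 4. Apply it to utilization and to satisfaction, and for each to the UV exposure and protection indexes, which makes 2 × 2 = 4 estimates. Report the within-arm correlations alongside, and label the pooled across-arm correlation descriptive only. Include the e-pamphlet arm only for metrics recorded there in the same way as in the other arms (for example logins, if captured), and not for sections completed.

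The change takes a few sentences, with no new data and no change in sample size. The cost is a little precision. Where a metric is confined to the two websites, 960 of 1,200 completers contribute, and the null standard error of rho rises from about 1/√1199 = 0.029 to 1/√959 = 0.032. Stratifying removes the arm artefact only. The result remains an association, because motivated participants may both use the site more and change more.

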Efficacy. Skin cancer-related behavioral outcomes will initially be assessed at baseline and 3 months later. They will also be assessed within UV4.me2 via behavioral tracking. We will assess sun protection (e.g., sunscreen use, clothing, shade) and UV exposure (e.g., sunburns, intentional/incidental sun exposure, indoor tanning) using items adapted from Glanz and colleagues and Ingledew and colleagues that our team has cognitively tested and assessed psychometrically with young adults 123-125. Sunburns, indoor tanning, and sunless tanning will be secondary outcomes since engagement in these activities is less frequent than sun exposure and protection in general. Negative effects will be defined as an increase in sunburns. Several studies have demonstrated the reliability and validity of self-report questionnaires of UV exposure and protection compared to observation and objective measures with no systematic bias identified among various populations 126-130. As indicators of quality of life, we will inquire as to the amount of perceived benefits of and barriers to UV exposure and protection 62,131-134.

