Efficacy. We will compare demographics across randomization arms using chi-squares and ANOVAs for categorical and continuous data, respectively. The primary outcomes are baseline to 3-month changes in UV exposure and protection. We will use multivariable linear regression to compare the effectiveness of UV4.me2 with UV4.me, and UV4.me2 with the e-pamphlet. We will not compare UV4.me to the epamphlet because UV4.me compared to a control condition was established in the prior study. Covariates in these models will include study arm, recruitment month/season, US region, and demographic factors identified as significantly imbalanced across arms (confounders). Analyses will be performed separately for the two primary outcomes. Variance stabilizing transformations may be applied as needed. Hypothesis tests will be two-sided with a 1.25% Type I error to account for multiple testing (2 intervention comparisons x 2 outcomes). Based on our data, experience, the enhanced study procedures, and the consumer research panel's experiences with young adults, we anticipate attrition of approximately 20% at each time-point. With 1500 young adults at baseline, we anticipate collecting 3-month follow-up data from 1200 participants, with 240 from the e-pamphlet arm and 480 participants from each of the other arms. The means (SDs) of the baseline to 3-month changes in UV exposure and protection indexes from the prior study control arm were 0.34 (0.74) and -0.37 (0.90), respectively. Given these parameters, we will have 80% power to detect small standardized effect sizes of 0.22 between the UV4.me2 and UV4.me arms, and 0.26 between the UV4.me2 and the e-pamphlet. These correspond to small detectable differences between intervention arms of 0.16 and 0.19 in baseline to 3-month changes in UV exposure and protection indexes, respectively. We will be able to detect slightly larger differences when the UV4.me2 and e-pamphlet arms are compared (detectable differences - UV exposure: 0.20; protection: 0.24). Analyses will assume that missingness depends on observed data (i.e., missing at random; MAR) 141. For drop-outs, the reason for attrition will be analyzed if available to search for evidence of informative missingness. Baseline variables will be compared by whether participants drop out or not. Significant variables will be added to the model to strengthen our MAR assumption. As a sensitivity analysis, we will use a shared parameter model with the assumption of missing not at random 142. If large changes in parameter estimation are found, we will use the results from the shared parameter model.

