Cost. We will estimate mean and median costs for each intervention. We will distinguish between development costs (one-time capital investment or "sunk" costs) and implementation costs, or the costs to maintain the interventions. We will also denote whether costs are related to research or intervention delivery. Analyses will distinguish between fixed costs (costs that do not vary with enrollment, e.g., server maintenance, data storage), and variable costs, which increase with additional participants. Because most costs are expected to be fixed, the mean cost per participant will be driven largely by the number enrolled. To explore costs of scale-up, we will conduct sensitivity analyses around additional dissemination efforts and higher take-up rates. We will also estimate the cost-effectiveness of UV4.me2 relative to the other conditions, calculating cost-effectiveness ratios as the difference in estimated costs divided by the difference in estimated effectiveness to determine the incremental cost per sunburn (or incident of UV exposure) averted for each intervention pair 141,142. We will also assess and estimate medical cost (e.g., OTC medication use, healthcare visits) offsets resulting from averted sunburns. To estimate longer-term cost-effectiveness, we will develop an Excel-based model to estimate qualityadjusted life year (QALY) gains associated with each sunburn (which increases melanoma risk) averted. For the cost-effectiveness modeling, we will use data from the literature on the probability of developing various forms of skin cancer as a result of sunburns and on QALY losses associated with various cancer outcomes to estimate the cost per QALY gained. Expressing cost-effectiveness as cost per QALY gained will facilitate comparison of the UV4.me2 intervention with other preventive health interventions. For all

cost-effectiveness analyses, we will perform one-way (and n-way) sensitivity analyses to examine the impact of varying input values over a plausible range.

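### The cost-effectiveness ratios have no planned sampling interval, and no rule covers an effectiveness difference that is near zero or negative

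*Combined protocol and SAP*

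**What the plan says.** Section 13.2 (Cost) sets out the analysis in four steps.

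- Costs: "We will estimate mean and median costs for each intervention". No standard error or interval is named. The section adds: "Because most costs are expected to be fixed, the mean cost per participant will be driven largely by the number enrolled".
- Ratio: it is formed by "calculating cost-effectiveness ratios as the difference in estimated costs divided by the difference in estimated effectiveness", and expressed as the "incremental cost per sunburn (or incident of UV exposure) averted for each intervention pair". No time horizon is given. The two citations on this sentence (141 and 142) resolve in the reference list to a missing-data textbook and a paper on informative dropout, so they do not supply a method for the ratio.
- Longer term: "we will develop an Excel-based model to estimate qualityadjusted life year (QALY) gains associated with each sunburn" averted, using literature inputs for cancer risk and QALY loss.
- Uncertainty, for all cost-effectiveness analyses: "we will perform one-way (and n-way) sensitivity analyses to examine the impact of varying input values over a plausible range". Separate sensitivity analyses cover wider dissemination and higher take-up.

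The Cost paragraphs of Sections 4.4.2 and 13.2 name no confidence interval, bootstrap, net-benefit analysis, acceptability curve or probabilistic run.

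Section 4.4.1 gives sunburn a lower rank: "Sunburns, indoor tanning, and sunless tanning will be secondary outcomes since engagement in these activities is less frequent". The documents state no sunburn rate, SD or power. The between-arm comparisons of behaviour described in Section 13 are for the UV exposure and protection outcomes.

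**The concern.** The denominator of each ratio is an estimate from this trial and has sampling error. Moving inputs over a range that the analyst considers plausible shows how sensitive the ratio is to those inputs. It does not show how precisely the trial has estimated the ratio, unless the range is tied to the standard error of the effect, and the plan does not tie it.

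Ratios also behave badly when the denominator is small. As the effect difference approaches zero the ratio grows without limit. Once the difference turns negative, the sign of the ratio no longer identifies the result: a negative ratio can mean cheaper and better, or dearer and worse. The plan does not say what will be reported in either case.

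At stake is Hypothesis 5 in Section 2.3, which asks whether UV4.me2 and UV4.me justify their extra cost, and the cost per QALY that Section 13.2 wants to set beside other preventive programmes. Neither can be judged from a point ratio without a statement of its precision.

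**Working it through.** **Inputs.** Section 13.1: 480, 480 and 240 participants at 3 months; standardized detectable effects 0.22 (UV4.me2 v UV4.me) and 0.26 (UV4.me2 v e-pamphlet) with 80% power; tests "two-sided with a 1.25% Type I error to account for multiple testing"; SDs of change 0.74 and 0.90. Section 13.2: 307, 307 and 154 at 12 months.

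**Reproducing the plan's own figures.** In SD units SE = sqrt(1/n1 + 1/n2), and the detectable effect is (z_0.99375 + z_0.80) × SE = (2.498 + 0.842) × SE.

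- 480 v 480: SE = 0.0645, detectable effect 0.216. Times 0.74 and 0.90 this is 0.16 and 0.19.
- 480 v 240: SE = 0.0791, detectable effect 0.264. Times 0.74 and 0.90 this is 0.20 and 0.24.

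These agree with the stated values, so the same SEs can be used for the precision of an effect difference.

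**What that precision does to a ratio.** Hold the cost difference fixed and positive. The 95% CI of the effect difference d is d ± 1.96 × SE, and the ratio at each limit is its point value times d/limit. The effects are illustrations on the UV-index SD scale, not forecasts.

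| Comparison | Observed d (SD) | 95% CI of d | Ratio, relative to its point value |
|---|---|---|---|
| 3 months, 480 v 480 | 0.22 | 0.093 to 0.347 | 0.63 to 2.35 (3.7-fold) |
| 3 months, 480 v 240 | 0.26 | 0.105 to 0.415 | 0.63 to 2.48 (about 4.0-fold) |
| 3 months, 480 v 480 | 0.10 (assumed) | -0.027 to 0.227 | 0.44 to no finite upper limit |
| 12 months, 307 v 307 | 0.22 | 0.062 to 0.378 | 0.58 to 3.56 |
| 12 months, 307 v 154 | 0.26 | 0.066 to 0.454 | 0.57 to 3.91 |

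The 12-month rows are included because the horizon of the ratio is not stated.

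**How often the ratio would have no bounded interval.** This happens when |d|/SE < 1.96, with probability Φ(1.96 - δ/SE) - Φ(-1.96 - δ/SE) for a true effect δ.

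- δ equal to the detectable effects 0.22 and 0.26: 7% and 9% at 3 months, 22% and 25% at 12 months.
- δ = 0.10 (assumed): 66% and 76% at 3 months, 76% and 83% at 12 months.

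**Sunburn.** The documents give nothing from which to compute this. Under assumed comparator means of 0.3 to 1.5 sunburns per person, a 10% to 20% reduction, and variance equal to the mean or to mean + mean², with 3-month numbers:

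- Most favourable (mean 1.5, 20% reduction, variance equal to the mean, 480 v 480): difference 0.30, SE 0.075, probability of no bounded interval 2%.
- Least favourable (mean 0.3, 10% reduction, larger variance, 480 v 240): difference 0.03, SE 0.048, probability 90%, with a 27% chance that the estimated difference has the wrong sign.

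The width of that range shows that the documents do not settle the question for sunburn.

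**The case against.** The strongest reply is that the effectiveness difference is itself an input. If its range were set at its 95% confidence limits, the one-way analysis would carry that sampling error into the ratio. With cost held fixed and limits that exclude zero, it would reproduce the bounded intervals in the table. This stands in part. It rules out the stronger reading that the ratios must carry no sampling uncertainty at all. But the plan does not say that the ranges will be set this way. The device also breaks down when the limits span zero, and it gives no joint interval once person-level costs or QALY inputs vary too.

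A second reply is that most costs are expected to be fixed. Section 4.4.2 takes labor and non-labor costs from staff questionnaires and billing records, so from the payer perspective there may be little individual cost to resample. This also stands. The correlation of cost and effect within participants matters mainly where participant time is valued (societal perspective) and where medical-cost offsets are counted.

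A third is that a reader might infer from Section 4.4.1 that the sunburn denominator will be close to zero, or apply the 3.7-fold and 4.0-fold ranges to cost per sunburn averted. The documents support neither. Lower frequency alone does not make a difference near zero, and 0.22 and 0.26 are detectable effects on the UV indexes, not expected effects on sunburn.

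Finally, net benefit needs a willingness-to-pay value, and none is given for a sunburn averted. That is a reason to report over a stated range, or to show a cost-effectiveness plane, rather than to omit the uncertainty.

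**Conclusion.** The concern holds in a limited form. The planned uncertainty analysis is one-way and n-way variation over ranges of unspecified origin. As written it provides no sampling interval for the ratios and no rule for an effectiveness difference that is near zero or negative.

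The roughly 3.7-fold and 4.0-fold ranges show scale only. They assume observed differences equal to the detectable effects, the UV-index SD scale, 3-month numbers and fixed cost. The 0.10 SD case is an assumption chosen to show when the upper limit is lost. The size of the problem for cost per sunburn averted cannot be computed from the documents.

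Cost is Secondary Aim 3, so the primary tests, the sample size and data collection are unaffected. What is affected is the strength of any conclusion on Hypothesis 5. This is an improvement worth making, not a defect that threatens the trial.

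**What to change.** Add the following to Section 13.2 (Cost) before the outcome data are analysed by arm.

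1. State the time horizon of each ratio and the source of every input range.
2. Bootstrap participants within arm. Resample each person's effect together with whatever person-level costs exist (participant time for the societal perspective, medical-cost offsets), and hold fixed program costs constant.
3. Report the cost difference and the effect difference, each with a 95% CI.
4. Report incremental net benefit, λ × (effect difference) - (cost difference), with a 95% CI over a stated range of willingness-to-pay values λ. Net benefit stays well defined when the effect difference crosses zero. When the effect interval includes zero, give this, or a cost-effectiveness plane, in place of a bare ratio.
5. Run the QALY model probabilistically, drawing the trial effect from its sampling distribution and the literature inputs from stated distributions.
6. Keep the one-way and n-way analyses as a supplement.

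The cost is a little more analysis work on data that will be collected anyway, and a result that may look less decisive than a single ratio.
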